9.5 Monitoring

The study will be reviewed at least annually by the NIAID Co-Infections and Complications DSMB, starting 6-12 months after the accrual of the first participant. As a proof-of-concept study in comparison between Arms A and B, formal interim analyses to conclude early superiority of immediate cryotherapy in reducing the cumulative rate of CIN2+ over 2 years will not occur. To consider futility, the DSMB will review the rates and predicted confidence bounds using the accumulated data and the simulated data for the unobserved remainder under the observed trend and under the design assumptions. The DSMB will review the AEs related to cryotherapy and overall reported AEs in the study arms. The DSMB will also review early discontinuation rates in the study arms and the reasons for discontinuation. The DSMB will also review baseline data critical to our sample size calculations including proportion diagnosed with CIN2+ in the control arm at entry which we assume to be 17%.

Reports on toxicity events will be provided to the DAIDS Medical Officer following the standard schedule for DSMB-monitored studies. Frequent reports on accrual and the conduct of the study will be provided to the protocol team. The schedules and formats of these reports will be outlined in the study monitoring plan.

9.6 Analyses

9.6.1 Comparison of CIN2+ between Arms A and B

For the primary analysis, time-to-event methods will be used to estimate the cumulative rate of the primary endpoint (from week 26 to week 130 after study entry) to account for lost to follow-up. The protocol team plans to use the Turnbull estimation for the proportions of participants without CIN2+ diagnosis by the end of the study, stratified by the study stratification factors [43]. The generalized Greenwood's formula for the standard error will be used for the variance and inverse variance method to account for strata [44]. The proportions in Arms A and B will be compared using asymptotic normal distributions. A one-sided 95% upper confidence bound on the difference (Arm B proportion minus Arm A proportion) between these proportions will also be provided. A stratified log-rank test will be conducted as a secondary analysis to compare the time to development of CIN2+ between Arms A and B. The primary analysis will be conducted as intent-to-treat on all participants randomized to the study Arms A and B. In other words, participants will be included in the analyses even if cryotherapy is not performed in Arm A and participants do not adhere to the strategy in Arm B. Per-protocol analysis will also be performed on only the participants who adhere to the specified procedures in Arms A and B, as secondary analysis. Participants without complete biopsy data will be censored at their last visit with a biopsy result (i.e., weeks 26, 78, 130).

Participants in Arm B may have biopsy done prior to week 26 based on the evaluation of baseline abnormal cervical cytology, whereas participants in Arm A will not have biopsies until week 26. Participants in Arm B diagnosed prior to their week 26 visit with CIN2+ that is cleared according to the biopsy at their week 26 will not be considered failures for the primary endpoint analysis. They are counted as meeting the primary endpoint only if CIN2+ is found at week 26 or later. Unplanned biopsies in Arm A that occur prior to the week 26 visit will not be considered for the primary endpoint.

The pathologic classification for the primary endpoint will be the determination by the local review at a DAIDS-assessed laboratory. Central review will be done for quality assurance.

9.6.2 Analyses of Secondary Endpoints

Secondary objectives will be evaluated with 2-sided tests or 2-sided confidence intervals with a significance level of 5%. The study is not powered to test the secondary study objectives formally, and no adjustment will be made to the type I error rates to account for multiple testing.

9.6.2.1 Arms A and B Only

The primary endpoint analysis method will be applied using an endpoint of CIN3+ (CIN3 or invasive cancer), as determined by local review at a DAIDS-assessed laboratory.

The targeted AEs reported after cryotherapy (Arm A) will be described separately. The study discontinuation rates will be compared between Arms A and B, using Fisher's exact tests, and time to discontinuation will be compared using a log-rank test. The reasons for study discontinuations will also be summarized.

The proportions of participants with hr-HPV detection by aHPV will be compared between Arms A and B at each study visit after study entry using Fisher's exact tests. Logistic mixed effects models will be developed for the longitudinal data on detection of hr-HPV at post entry visits to make a comparison between Arms A and B. These models will explore nadir CD4 count and baseline/screening characteristics (e.g., HIV RNA level and cytology outcome) as independent variables. Similar analyses will be conducted to assess cytological abnormalities.

Within Arm A, cryotherapy outcomes will be assessed using McNemar's test for correlated proportions. Proportions of participants with and without cytological abnormalities at baseline and at 26 weeks after cryotherapy will be estimated. The HPV types detected at the time of abnormalities will also be summarized.

Time to CIN2+ diagnosis will be compared between those with and without detection of hr-HPV by aHPV and by *care*HPV at 26 weeks after cryotherapy, using a log-rank test in Arm A. It will also be compared between those with and without cervical cytological abnormality at 26 weeks after cryotherapy.

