1.3 Secondary Objectives

- 1.3.1 To evaluate the safety and tolerability of cervical cryotherapy (Arm A) in HIV-infected women.
- 1.3.2 To compare between arms the presence of cervical cytological abnormalities during the study.
- 1.3.3 To assess study discontinuation rates and reasons for discontinuation between arms.
- 1.3.4 To compare time to development of CIN2+ between those women with and without detection of hr-HPV by aHPV at 26 weeks, and those women with and without cervical cytological abnormalities after cervical cryotherapy in Arm A.
- 1.3.5 To assess detection frequencies of cervical HPV types (by DNA PCR) and the rates of hr-HPV by *careHPV* at study entry.
- 1.3.6 To evaluate baseline/screening characteristics (detection of various HPV types, CD4, CD4 nadir, and HIV RNA) associated with cytological abnormalities at baseline.

PEPFAR Objectives

- 1.3.7 To evaluate the sensitivity and specificity of *careHPV* for hr-HPV detection as measured by aHPV and HPV DNA PCR at study screening and the agreement beyond chance between these measures.
- 1.3.8 To report the proportion of HIV-infected women with extensive cervical lesions inappropriate for cryotherapy and examine possible factors associated with these lesions including CD4 count, plasma HIV-1 RNA, ART use and HPV types detected.

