2.2 Rationale

Age Range

HPV testing is used in the screening algorithm of HIV-uninfected women age 30 or older. HPV testing has not been traditionally used for younger women because of the high-incidence of transient, insignificant HPV infections. However, HIV-infected young people have been noted to have a high prevalence of CIN2/3 as well as cases of invasive cancer. Therefore, the protocol team has opted to include younger women in this study.

Arm C

Women falling into either of the following two categories will be followed in Arm C: (i) women who have extensive cervical lesions that are inappropriate for cervical cryotherapy and (ii) high-risk HPV negative women with cervical lesions or a HSIL cytology. In a large screen-and-treat evaluation from Zambia, approximately 15% of women undergoing evaluation were thought to have lesions inappropriate for cryotherapy and were referred for LEEP [40]. In a recent presentation from Zambia, 20% of HIV-infected women had lesions inappropriate for cryotherapy. Of these women, 15%

had invasive cancer and another 33% had CIN2 or 3. Inclusion of this category of women in the present study will yield a larger number of participants for assessment of the HPV genotypes found in CIN2+ biopsy specimens (possible future study) and for the effect of LEEP on prevalent hr-HPV infections. In addition, these study populations will provide important data for implementation of the HPV test-and-treat strategy, as outlined in section 1.3.8, including the role of HPV testing in the management of women presenting with such conditions.

PEPFAR Objectives

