3.0 STUDY DESIGN

A5282 is a randomized clinical trial of an HPV test-and-treat-strategy compared to cytology-based strategy. The study population is composed of HIV-1-infected women ages 18 years or older. No restrictions are in place for ART regimens, which will be initiated or continued according to the local standard of care. Sites should strongly consider initiating ART in women with a CD4 <350 cells/ μ L, if feasible. ART is not provided by the study. To be eligible, participants must have no history of cervical, vaginal, or vulvar cancer; no prior cervical cryotherapy, cervical conization, or hysterectomy; and no prior receipt of HPV vaccines.

The screening laboratory evaluations include CD4 cell count, plasma HIV-1 RNA viral load, and complete blood count. All participants will undergo a speculum examination at screening to obtain cervical specimens for cytology, aHPV, and HPV DNA PCR. Participants will be screened for hr-HPV with aHPV. This test semi-quantitatively detects the presence of type 16, type 18, or the presence of any of the other 12 types of hr-HPV (31, 33, 35, 39, 45, 51, 52, 56, 58, 59, 66, and 68). A separate specimen will be collected and stored for *careHPV* testing, which detects the 14 types listed above.

At screening, the examiner will also perform a visual inspection and colposcopy without biopsies to determine whether the candidate's cervix is suitable for cryotherapy. Participants with cervical lesions inappropriate for cryotherapy (as defined in Section 4.1.8) are not eligible for randomization but will be eligible to register to Arm C. Participants without hr-HPV (by aHPV) will also be eligible to register to Arm C if lesions were seen on the screening colposcopy or if the screening cytology shows HSIL.

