#### **4.2.5 Secondary endpoint:** Cervical cytology results at study visits

Table (based on arms A and B): Cytology results (normal, abnormal:LSIL, abnormal:HSIL) at study visits with p-value from Fisher's test.

Table (based on arm A only): (Crosstabulation of) Cytology results at baseline and week 26 with p-value from McNemar's test.

Tables (based on arms A and B cytology results after study entry): Results of longitudinal logistic mixed effects models with independent variables nadir CD4 count, baseline/screening characteristics (e.g., HIV RNA level, current CD4 count, sexual history and cytology outcome) and recent sexual activity (time-updated variables on number of vaginal sex partners and frequency of condom use within the previous 6 months) **[EXPLORATORY]**

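### The Arm A-only McNemar p-value for cytology should be labelled descriptive, and the week-26 comparison of arms should adjust for baseline cytology and ART stratum

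*Protocol*

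**What the plan says.** Secondary objective 1.3.2 is a between-arm one: "To compare between arms the presence of cervical cytological abnormalities during the study". For hr-HPV, Protocol 9.6.2.1 plans Fisher's exact tests of Arm A against Arm B at each post-entry visit, and then, for the same two arms: "Logistic mixed effects models will be developed for the longitudinal data on detection of hr-HPV at post entry visits to make a comparison between". It extends this plan to cytology: "Similar analyses will be conducted to assess cytological abnormalities". The next paragraph adds the within-arm analysis: "Within Arm A, cryotherapy outcomes will be assessed using McNemar's test for correlated proportions", with the proportions abnormal at baseline and 26 weeks after cryotherapy to be estimated.

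SAP 4.2.5 lists three items on cytology:

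1. For Arms A and B: "Cytology results (normal, abnormal:LSIL, abnormal:HSIL) at study visits with p-value from Fisher's test".
2. For Arm A only, a cross-tabulation: "Cytology results at baseline and week 26 with p-value from McNemar's test".
3. Longitudinal logistic mixed models for Arms A and B, marked exploratory. The listed independent variables include baseline cytology, nadir and current CD4, HIV RNA, sexual history and recent sexual activity. Arm is not in the list, and neither is ART use.

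Protocol 9.6.2 sets two-sided 5% tests for secondary objectives, without multiplicity adjustment, and says the study is not powered to test them formally.

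**The concern.** McNemar's null hypothesis is that the proportion abnormal did not change between two times. That differs from the hypothesis that cryotherapy had no effect. The protocol's label, cryotherapy outcomes, invites the second reading. The documents give three other reasons why cytology could change in Arm A:

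- **Natural change.** All randomized women enter hr-HPV positive and the age range starts at 18. Protocol 2.2 refers to a "high-incidence of transient, insignificant HPV infections" in younger women.
- **ART.** Protocol 3.0 says "Sites should strongly consider initiating ART in women with a CD4" below 350 cells/μL, so some women may start ART between the two smears.
- **Entry biopsies.** Letter of Amendment #1 adds one or two biopsies, taken from visible lesions where there are any, immediately before the freeze.

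A small p-value could therefore be reported as cryotherapy clearing abnormal cytology when the test cannot show that. An underlying worsening could equally hide a benefit. Arm B has cytology on the same schedule (Protocol 6.1), but the baseline-by-week-26 table is planned for Arm A only.

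**Working it through.** **1. Inputs.** The documents give no power or expected rate for any cytology analysis, so there is no plan figure to reproduce.

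- Women per arm: 140 enrolled (Protocol 9.4). With the stated 20% loss, 140 × 0.8 = 112.
- Baseline abnormal cytology π: 40-60%, assumed. Protocol 2.1 reports 50% at the Johannesburg site, among HIV-infected women in general.
- Clearance by week 26, c: 20-50%. New abnormality among women with normal smears, i: 10-20%. Both are assumed.
- Cytology is treated as abnormal or normal.

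**2. McNemar in Arm A, with natural change only.** The discordant probabilities are p10 = πc (abnormal to normal) and p01 = (1 − π)i (normal to abnormal). The statistic is (b − c′)²/(b + c′), where b and c′ are the two discordant counts; the 5% cut is 3.84.

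Take π = 0.5, c = 0.4, i = 0.1. Then p10 = 0.20 and p01 = 0.05.

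- n = 112: expected counts 22.4 and 5.6, giving 16.8²/28 = 10.1.
- n = 140: expected counts 28 and 7, giving 21²/35 = 12.6.

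Over 40,000 simulated trials per setting, the exact two-sided test gives p<0.05 in 88% (n = 112) and 94% (n = 140). With π = 0.5 and c = i = 0.2, both discordant probabilities are 0.10 and the rate is 3%. With π = 0.6, c = 0.5, i = 0.1 it exceeds 99%.

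The same point with the size of the fall fixed (n = 125, 15-25% of normal smears becoming abnormal, chi-square version):

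| Assumed unaided fall | McNemar p<0.05 |
|---|---|
| 50% to 45% | 17-25% |
| 50% to 40% | 47-63% |
| 60% to 50% | 54-70% |
| 15 points, from 50% or 60% | 77-92% |

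**3. Fisher, Arm A against Arm B.** In the settings of step 2 with n = 112 or 140 and no difference between the arms, Fisher's test rejects in about 3-5% of trials. The planned between-arm test is therefore valid.

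**4. What each planned cytology analysis uses.**

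| Analysis | Compares arms | Baseline cytology | ART stratum |
|---|---|---|---|
| Fisher by visit | yes | no | no |
| McNemar, Arm A | no | yes, paired | no |
| Mixed models, protocol | yes | yes | not named |
| Mixed models, SAP (exploratory) | arm not named | yes | not named |

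Fisher is thus the only SAP cytology analysis that expressly compares the arms, and it leaves out the strongest available covariate.

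**5. What adjustment is worth.** An illustration on assumed rates: 125 per arm, 50% abnormal at baseline; in Arm B 60% of abnormal smears stay abnormal and 15% of normal ones become abnormal; in Arm A both odds are halved. Week-26 abnormality is then 0.5 × 0.60 + 0.5 × 0.15 = 37.5% in Arm B and 0.5 × 0.429 + 0.5 × 0.081 = 25.5% in Arm A. Over 3,000 simulated trials, power is 47% for Fisher, 52% for unadjusted logistic regression and 60% with baseline cytology added. The gain over Fisher is 13 points, of which about 8 come from the baseline adjustment and the rest from Fisher's conservatism. Across moderate settings the gain is about 8 to 13 points. It is larger, near 20, if 70% of abnormal smears persist and only 10% of normal ones become abnormal. The ART stratum was not simulated.

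**The case against.** The strongest reply is that the randomized comparison is already in the plan. The sentence before the McNemar paragraph extends the between-arm tests and models to cytology, objective 1.3.2 is itself between-arm, and the SAP lists the Fisher table first. A reader might infer that cryotherapy's effect on cytology is judged only by the before-after test and that the control arm goes unused. The documents do not support that. Nor do they say anywhere that the McNemar result will carry a causal claim.

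A reader might also take the McNemar rejection rates as an inflated type 1 error. They are not. Where a real fall is assumed, McNemar's own null is false and the rejections are power to detect that fall. The rates depend wholly on assumed transitions.

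The evidence for natural clearance is also limited. The remark on transient infections explains why HPV testing was not traditionally used in younger women, and it follows a sentence about HIV-uninfected women. Protocol 2.1 says women with HIV are more likely to have persistent hr-HPV infection. The direction of natural change is therefore uncertain.

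Finally, omitting baseline cytology from Fisher costs precision and does not cause bias. Arm B is an active strategy, with colposcopy and biopsies after abnormal cytology and LEEP for CIN2+. No comparison of the arms can separate cryotherapy from the Arm A entry biopsies.

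All of this stands, and it limits the point. It leaves three things open: an unlabelled p-value under the name of cryotherapy outcomes, a two-way table for one arm only, and SAP models that no longer name the comparison the protocol assigns to them.

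**Conclusion.** The point holds as one of labelling and efficiency in a secondary analysis. The Arm A McNemar p-value measures change over time and supports no inference about cryotherapy. The planned Fisher tests are sound but use neither baseline cytology nor the ART stratum, and the SAP mixed models need arm named to match the protocol. On moderate assumed rates, adjusting for baseline cytology is worth about 8 to 13 points of power at week 26; the documents give no transition rates from which to fix the figure. The primary CIN2+ comparison is not affected.

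**What to change.** In SAP 4.2.5, and in Protocol 9.6.2.1 if it is amended:

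1. Show the baseline-by-week-26 cytology table for both arms.
2. Label the Arm A change as descriptive, and state that no treatment inference is drawn from its McNemar p-value (or omit the p-value).
3. Base the week-26 cytology comparison on a logistic regression of abnormality on arm, baseline cytology and ART stratum. The Fisher tables by visit can stay.
4. Name arm as an independent variable in the cytology mixed model.
5. State that the comparison is between strategies (cryotherapy with entry biopsies against cytology with colposcopy and LEEP as needed) and does not isolate cryotherapy.

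The cost is a few lines of SAP text, one table and one regression on data already collected. No visit, specimen or sample size changes.

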9.6.2.2 Arms A, B and C

The frequencies of HPV types by DNA PCR and the rate of hr-HPV by aHPV and *care*HPV detected at screening will be summarized. Detection rates of multiple HPV types will also be described. Logistic regression models will be developed to explore the factors associated with cytological abnormalities at entry or screening, e.g., HPV types, CD4, nadir CD4, and HIV RNA level.

The sensitivity and specificity of *care*HPV for hr-HPV detection will be assessed based on aHPV results and HPV DNA PCR results on the types included in *care*HPV, using the screening data. The agreement between the *care*HPV and aHPV, and *care*HPV and HPV DNA PCR methods for categorizing the HPV type, beyond what would be expected by chance, will be estimated with Cohen's *Kappa* statistic [45].

The targeted AEs reported after LEEP in all study arms will be described.

We will report the proportion of women with cervical lesions inappropriate for cryotherapy. We will report the prevalence of CIN2+, hr-HPV test results, and cytological abnormalities in these women. Specifically, we will assess the sensitivity, specificity, positive and negative predictive value of hr-HPV detection by careHPV and aHPV for CIN2+ in this subgroup. We will explore the inter-rater reliability of such assessments by blinded review of digital colposcopic images. We will assess the relationship of CD4 cell count (<200, 200-349, 350-499, ≥500), ART use (yes or no), and plasma HIV RNA to the presence of these lesions.

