The study will randomize 280 participants with hr-HPV (by aHPV) to Arm A or Arm B. Randomization will be stratified by current use of ART (i.e., any ART or no ART) with institutional balancing. Participants in Arm A (HPV test-and-treat) will undergo cervical cryotherapy at entry. Participants in Arm A will receive the results of the cytology, but participants will receive cryotherapy treatment regardless of the results. Participants in Arm B will follow a cytology-based management plan involving three steps – cytology, colposcopy with directed biopsies, and LEEP (as needed). Participants in Arms A and B will be seen at regular intervals post entry for aHPV, HPV DNA PCR, cervical cytology, and cervical colposcopy and directed biopsies for a total follow-up length of 130 weeks. A separate specimen will be collected 26 weeks post entry and stored for *careHPV* testing.

Participants in Arm C will undergo colposcopy and directed biopsies. If CIN2+ is found by biopsy, then LEEP will be performed and a follow-up visit 26 weeks after these procedures will be scheduled for aHPV, HPV DNA PCR, *careHPV*, cervical cytology, and cervical colposcopy and directed biopsies. After the week 26 visit, Arm C participants will go off study.

All participants undergoing cryotherapy or LEEP will be seen 4 weeks post-procedure to assess for AEs from the procedure. Quality assurance procedures are in place for reviews of digital impressions rendered during colposcopies (no lesions seen, lesions seen/appropriate for cryotherapy or lesions seen/not appropriate for cryotherapy). Slides from biopsies with and without CIN2+ will be reviewed regionally or centrally (see the A5282 Manual of Procedures [MOPS] for details). HPV DNA PCR and *careHPV* will be performed on stored specimens and results will not be used for clinical management.

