4.0 SELECTION AND ENROLLMENT OF PARTICIPANTS

4.1 Inclusion Criteria

4.1.1 HIV-1 infection, documented by any licensed rapid HIV test or HIV enzyme or chemiluminescence immunoassay (E/CIA) test kit at any time prior to study entry

and confirmed by a licensed Western blot or a second antibody test by a method other than the initial rapid HIV and/or E/CIA, or by HIV-1 antigen, plasma HIV-1 RNA viral load.

NOTE: For sites located in countries other than the United States, the term "licensed" refers to a kit that has been certified or licensed by an oversight body within that country and validated internally.

World Health Organization (WHO) and Centers for Disease Control and Prevention (CDC) guidelines mandate that confirmation of the initial test result must use a test that is different from the one used for the initial assessment. A reactive initial rapid test should be confirmed by either another type of rapid assay or an E/CIA that is based on a different antigen preparation and/or different test principle (e.g., indirect versus competitive), or a Western blot or a plasma HIV-1 RNA viral load.

4.1.2 The following laboratory values obtained within 30 days prior to study entry:

- Absolute neutrophil count (ANC) $\geq 750/\text{mm}^3$
- Platelet count $\geq 75,000/\text{mm}^3$
- Hemoglobin (HgB) $> 8 \text{ gm/dL}$

4.1.3 For candidates suitable for cervical cryotherapy (as defined in section 4.1.8 below), hr-HPV detected by aHPV within 30 days prior to study entry.

NOTE: Participants with a visual inspection showing extensive lesions inappropriate for cryotherapy do not require an aHPV test result prior to enrollment.

4.1.4 For women without hr-HPV detected by aHPV, presence of lesions on visual inspection or HSIL cervical cytology.

4.1.5 Suitable candidate for cervical cryotherapy, defined as:

- No visible cervical lesions.
-- OR --
- Any visible lesions are located entirely on the ectocervix and are no more than 2 to 3 mm into the endocervical canal, AND
- visible lesions cover less than 75% of the cervix, AND
- all visible lesions are deemed appropriate for cryotherapy by the treating health care provider.

NOTE: Participants with cervical lesions inappropriate for cryotherapy are not eligible for randomization and should be followed in Arm C.

4.1.6 For participants of reproductive potential, negative serum or urine pregnancy test with a sensitivity of $<25 \text{ mIU/mL}$ within 48 hours prior to study entry.

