6.2 Timing of Evaluations

6.2.1 Screening Evaluations

Screening evaluations must occur prior to the participant's starting any study treatment. Screening evaluations to determine eligibility must be completed within 30 days prior to study entry, unless otherwise specified.

The cytology and HPV evaluations cannot be performed while the participant is menstruating. If a participant has visual evidence of bacterial STIs or an examination consistent with pelvic inflammatory disease, then samples for cytology and HPV testing should not be obtained. The participant should be treated according to the local standard of care, in which case screening evaluations can be performed a minimum of 7 days after initiating treatment.

In addition to data being collected on participants who enroll into the study, demographic, clinical, and laboratory data on screening failures will be captured in a Screening Failure Results form and entered into the ACTG database. Cytology, colposcopic visual impression, and HPV testing on screening failures will also be captured on a case report form (CRF) and entered into the ACTG database.

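### Section 9.6.2.2 models abnormal cytology on HPV types in Arms A, B and C, but hr-HPV-negative women are enrolled only with a lesion or HSIL, so contrasts against them are likely biased downward

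*Protocol*

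**What the plan says.** Protocol objective 1.3.6 reads: "To evaluate baseline/screening characteristics (detection of various HPV types, CD4, CD4 nadir, and HIV RNA) associated with cytological abnormalities at baseline". Letter of Amendment #1 adds sexual history and recent sexual activity to the candidate factors. The matching analysis is under the heading "9.6.2.2 Arms A, B and C": "Logistic regression models will be developed to explore the factors associated with cytological abnormalities at entry or screening, e.g., HPV types". No weighting, restriction by HPV status or use of screening failures is stated for this model.

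The routes into the three arms are:

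- **hr-HPV-positive, suitable for cryotherapy.** Section 3.0: "The study will randomize 280 participants with hr-HPV (by aHPV) to Arm A or Arm B". No cytology result is required.
- **hr-HPV-negative.** Section 4.1.4: "For women without hr-HPV detected by aHPV, presence of lesions on visual inspection or HSIL cervical cytology". Section 3.0 sends these women to Arm C only: "Participants without hr-HPV (by aHPV) will also be eligible to register to Arm C if lesions were seen on the screening colposcopy". An HSIL smear at screening also qualifies.
- **Extensive lesions, whatever the HPV status.** Section 4.1.3, note: "Participants with a visual inspection showing extensive lesions inappropriate for cryotherapy do not require an aHPV test result prior to enrollment". This route also depends on a lesion.

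Section 6.2.1 provides that "Cytology, colposcopic visual impression, and HPV testing on screening failures will also be captured on a case report form (CRF". Demographic, clinical and laboratory data on screening failures are recorded as well. Section 2.2 says that all consenting women will be used, but only for the PEPFAR objectives. Objective 1.3.6 stands before the PEPFAR heading in section 1.3 and has no PEPFAR tag in SAP section 2.3.

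**The concern.** In the enrolled set, entry depends jointly on the exposure (hr-HPV status) and on something close to the outcome (HSIL, or a lesion that tends to go with an abnormal smear), and it does so only in the hr-HPV-negative group. Women with no hr-HPV, no lesion and no HSIL fail screening. They include most of the normal-smear women who would anchor an HPV-negative reference group. Those who remain have abnormal cytology more often than hr-HPV-negative women at large, so hr-HPV looks less strongly associated with abnormal cytology than it is.

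At stake is the reading of objective 1.3.6 for HPV. A report could show a weak, absent or even inverse association that comes from the enrolment rule.

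**Working it through.** **1. The plan's own figures.** Section 9.4 expects about 700 screened, of whom 40% are randomised: 700 × 0.40 = 280, as stated. Adding the Arm C maximum gives 280 + 170 = 450. So about 700 − 450 = 250 screened women lie outside Arms A to C. hr-HPV-negative women without a lesion or HSIL can only be among those 250. The documents do not say how many of the 250 they are.

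**2. Formula.** Let hr-HPV-positive women number *a* abnormal and *b* normal, and hr-HPV-negative women *c* abnormal and *d* normal. Assume entry of hr-HPV-positive women does not depend on cytology. Let s1 and s0 be the shares of hr-HPV-negative women with abnormal and with normal smears who meet the lesion-or-HSIL rule. Then

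OR(enrolled) = (a/b) / (c·s1 / d·s0) = OR(unselected) × s0/s1.

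With *h* the HSIL share of abnormal smears, L1 the lesion rate with lower-grade abnormal smears and L0 the lesion rate with normal smears:

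s1 = h + (1 − h)·L1 and s0 = L0.

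Every woman with HSIL qualifies. If lesions are at least as common with abnormal smears as with normal ones, s0 < s1 and the bias is downward. No outside figure is needed for that direction.

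**3. Unselected odds ratio.** Protocol section 2.1 (Johannesburg) gives 191 women with PCR results, 138 of them hr-HPV-positive, and 54 of 90 women with normal cytology positive. Assuming the 90 are among the 191:

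| | Abnormal | Normal |
|---|---|---|
| hr-HPV-positive | 138 − 54 = 84 | 54 |
| hr-HPV-negative | 53 − 36 = 17 | 90 − 54 = 36 |

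OR = (84/54) / (17/36) = 3.29 (95% CI 1.68 to 6.44).

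**4. Applying the entry rule.** The values of *h*, L1 and L0 are assumptions. The upper end for *h* matches the HSIL share of all abnormal smears in that cohort, 182/503 = 36%.

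- Base case, h = 20%, L1 = 40%, L0 = 10%: s1 = 0.20 + 0.80 × 0.40 = 0.52. Enrolled hr-HPV-negative women are 17 × 0.52 = 8.8 abnormal and 36 × 0.10 = 3.6 normal. OR = 3.29 × 0.10/0.52 = **0.63**.
- Range, h 10–36%, L1 30–60%, L0 5–20%. Lowest: s1 = 0.36 + 0.64 × 0.60 = 0.744, OR = 3.29 × 0.05/0.744 = **0.22**. Highest: s1 = 0.10 + 0.90 × 0.30 = 0.37, OR = 3.29 × 0.20/0.37 = **1.78**.
- Lesions unrelated to cytology, L1 = L0 between 10% and 30%. Lowest: s1 = 0.36 + 0.64 × 0.10 = 0.424, OR = 3.29 × 0.10/0.424 = **0.78**. Highest: s1 = 0.37, OR = 3.29 × 0.30/0.37 = **2.67**.

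Every value is below 3.29. The sign reverses when s0/s1 < 1/3.29 = 0.30. There is no distortion only if s0 = s1.

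**The case against.** The strongest reply is that the population is inferred from a heading. No sentence limits the model to enrolled women. The same heading also covers PEPFAR analyses that do use all consenting women, the outcome is described as being at entry or screening, and screening-failure results are collected. The cross-reference behind the all-consenting rule is also unstable: it points to section 1.3.5 in the base protocol and to section 1.3 in the later letter of amendment. This stands in part. The team may have meant all screened women, but the text extends that population only to the PEPFAR objectives, so the captured data are an available remedy and not the stated plan.

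Second, the SAP leaves this objective to previous analyses, whose population and coding are not in these documents. That stands. A reader might infer that a biased result has been produced; the documents do not show this.

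Third, the plan names HPV types, while the illustration is for any hr-HPV versus none. That stands too. A type-present versus type-absent term has a mixed reference group, partly hr-HPV-positive women with other types, and no figure is computed for it.

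Three stronger readings are tempting but unsupported:

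- *The entry criterion is the outcome.* The criterion is HSIL or a lesion; the outcome is any cytological abnormality. ASCUS or LSIL alone admits no hr-HPV-negative woman, and a lesion with a normal smear does. The two overlap but are not the same.
- *The CD4 and HIV RNA coefficients are driven down.* They could shift if they are related to HPV status, but neither size nor direction has been calculated.
- *All 250 non-enrolled women are the missing reference group.* That number pools every reason for not enrolling.

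**Conclusion.** The point holds for contrasts whose reference group includes hr-HPV-negative women, if the model is fitted on Arms A to C as the heading indicates. The bias is downward whenever hr-HPV-negative women with abnormal smears qualify for entry more often than those with normal smears, which is likely because HSIL alone qualifies. The illustration shows the bias could be large enough to hide or reverse the association, but it does not establish that hr-HPV will look protective: part of each range lies above 1.

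The size rests on lesion and HSIL rates that the documents do not give, on PCR counts from one site although entry uses aHPV, and on the 90 women being within the 191. Contrasts among hr-HPV-positive women are largely unaffected, apart from any effect of the Arm C cap. Section 9.6.2 describes the secondary objectives as not formally powered and not adjusted for multiplicity, and this model is exploratory. The randomised comparison of Arms A and B is untouched.

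**What to change.** 1. State in section 9.6.2.2 that the objective 1.3.6 models use all screened women with valid screening aHPV and cytology, including screening failures.
2. Fit models with covariates collected only at entry (the sexual behaviour questionnaire) in enrolled hr-HPV-positive women only, whatever their cytology. This set must not be narrowed by cytology, which would condition on the outcome.
3. Report no HPV-positive versus HPV-negative contrast from Arms A to C alone.
4. Confirm which population the previous analyses of this objective used. If it was Arms A to C, re-run them on all screened women or caveat the HPV result.

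The cost is a short addition to the text, a check of the completed analysis and possibly a re-run. The screening-failure cytology, HPV, clinical and laboratory data are already captured. The downside is that questionnaire covariates are missing for screening failures, so those factors can be studied only in the restricted set.
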